7.3.3	Post-COVID Functional Status.....	21
7.4	Significance.....	21
8	Safety Analysis	21
8.1	Primary Safety Endpoint	21
8.2	Secondary Safety Endpoints.....	22
8.2.1	Major or non-major clinically relevant bleeding through Day 30	22
8.2.2	Any bleeding through Day 8 and through Day 30	22
8.2.3	Other Adverse Events	22
8.3	Laboratory Data.....	23
9	Interim Analyses.....	23
10	Composite and Net Endpoints	23
11	Subgroup and Sensitivity Analyses	23
11.1	Primary Efficacy Endpoint Sensitivity Analysis.....	23
11.2	Primary Efficacy Endpoint Subgroup Analyses.....	23
11.3	Secondary Efficacy Endpoint Subgroup and Sensitivity Analyses	24
11.4	Additional Safety Analyses	24
12	Changes from Methods Planned in the Protocol	24
13	References.....	24
14	Appendix.....	25
14.1	COVID Severity Definitions	25
14.2	Descriptions of the Models and Methods Used.....	25
14.2.1	Bayesian Description	25
14.2.2	MI Description	25
14.2.3	Power Description.....	25

Approvals

Signatures		
Biostatistician (ARCA)	_____ [name]	_____ Date
Biostatistician (CPC)	_____ [name]	_____ Date
Principal Investigator	_____ [name], MPH	_____ Date
Chief Scientific Officer (ARCA)	_____ [name], PhD	_____ Date

Revision History

VERSION	DESCRIPTION OF CHANGE
1.0	Original
2.0	
 • Inserted language submitted in IND 150187, Sequence 0015 on 29 Nov 2021 containing Sponsor’s response to the Division’s review of Version 1.0 clarifying Wilcoxon Signed Rank will not be used in the primary efficacy endpoint analysis. • Added composite of clinical events as a secondary efficacy endpoint in Section 2.5.1. • Moved probability of discharge as assessed by ACTT from exploratory efficacy endpoint to secondary endpoint in Section 2.5.1 • Added multiplicity control description to Section 5.7 • Added Section 5.8 Transformations and Normality • Added Section 7.1.2 Secondary Analysis of the Primary Efficacy Endpoint • Added Section 7.2.3 Composite of Clinical Events • Added Section 10 Composite and Net Endpoints • Added Section 11 Subgroup and Sensitivity Analyses to provide additional description of how types of missingness will be addressed via multiple imputation. • Added Section 14.2 Description of Models and Methods which include descriptions of the Bayesian models, methods for multiple imputation, and methods for power analysis used in this study. • Added Section 12 Changes from Methods Planned in the Protocol to describe the key changes in either endpoint or analysis methodology.
3.0	
 • Corrected the censoring date for death in Section 7.2.2 to "day x+1, where x denotes the longest observation window among all subjects in the analysis" from “day of death”. This brings censoring date for death into alignment with the NAPc-201 clinical protocol language. • Added clarifying language to Section 7.2.3 regarding pre-existing organ support of any modality as an additional covariate, representing a special case arising from the specifications of the analysis.

List of Abbreviations

Abbreviation	Term
ACTT	Adaptive COVID-19 Treatment Trial
AE	Adverse Event
ATC	Anatomical Therapeutic Chemical
BMI	Body Mass Index
CEC	Clinical Endpoint Committee
CFR	Code of Federal Regulations
CI	Confidence Interval
CRF	Case Report Form
CSR	Clinical Study Report
CTMS	Clinical Trial Management System
DAPT	Dual Antiplatelet Therapy
DMP	Data Management Plan
DSMC	Data Safety Monitoring Committee
eGFR	Estimated Glomerular Filtration Rate
FDA	Food and Drug Administration
hsCRP	High Sensitivity C-reactive Protein
ICF	Informed Consent Form
IL-6	Interleukin-6
ITT	Intent-to-Treat
kg	Kilogram
LLN	Lower Limit of Normal
LMWH	low molecular weight heparin
MCAR	Missing Completely At Random
MedDRA	Medical Dictionary for Regulatory Activities
mg/dl	Milligram per deciliter
mITT	Modified Intent-to-Treat
mmHg	Millimeters of mercury

Abbreviation	Term
NSAIDS	Non-Steroidal Anti-Inflammatory Drugs
PCFS	Post-COVID Functional Status
PCR	Polymerase Chain Reaction
PT	Prothrombin Time
PTm	Preferred Term
PTT	Partial Thromboplastin Time
SAE	Serious Adverse Event
SAP	Statistical Analysis Plan
SC	Subcutaneous
SD	Standard Deviation
SoC	Standard of Care
SOP	Standard Operating Procedure
TEAE	Treatment-Emergent Adverse Event
TFLs	Tables, Figures, and Listings
UFH	Unfractionated Heparin
ULN	Upper Limit of Normal
URC	Unblinded Review Committee
WHO DDE	World Health Organization Drug Dictionary (Enhanced)

1 Introduction

The ASPEN-COVID-19 ("ASPEN") protocol comprises sequential Phase 2b and Phase 3 randomized, multicenter, active comparator studies evaluating the hypothesis that rNAPc2, a novel, potent and highly selective tissue factor inhibitor with anticoagulant, anti-inflammatory and potential antiviral properties, reduces elevated D-dimer levels (Phase 2b primary endpoint) and shortens time to recovery (Phase 3 primary endpoint) compared to heparin in hospitalized patients with COVID-19 and elevated D-dimer levels. Study participants and Clinical Endpoint Committee (CEC) members assessing the clinical endpoints are blinded to treatment assignment. Analysis of Phase 2b data could lead to study discontinuation, adjustment of eligibility criteria or sample size, and will inform the rNAPc2 dose regimen to be studied in Phase 3.

This statistical analysis plan (SAP) describes all study related details and statistical analyses and summaries to be generated on data collected from the Phase 2b ASPEN-COVID-19 study.

The SAP is designed to assist in the analysis of clinical study data for final reporting of the Phase 2b study. This content includes, but is not limited to, statistical analysis and summary of all endpoints identified in the study protocol, heretofore referred to as 'the study' or 'study.'

Details of reporting for the purpose of the Data Safety Monitoring Committee (DSMC) and other committees are documented elsewhere. Details of planned interim analyses are documented in the DSMC Charter and DSMC Reporting Plan. Reporting of the Phase 3 study will be documented in a separate analysis plan.

2 Study Design and Plan

2.1 Design and Primary Objectives

The primary objective of the Phase 2b study is to identify an rNAPc2 dosing regimen with an acceptable safety profile that reduces D-dimer levels compared to standard of care (SoC) heparin regimens. Secondary and exploratory objectives are to compare the treatment groups in terms of biomarkers associated with outcomes including those related to coagulation and inflammation, as well as for clinical and functional outcomes.

2.2 Sample Size Determination

During Phase 2b, approximately 160 participants will be enrolled and randomized 1:1:2 to rNAPc2 dose regimen 1, rNAPc2 dose regimen 2, and heparin SoC, respectively. Assuming approximately 20% of participants may not be evaluable for any reason, 160 randomized participants will provide for approximately 130 evaluable participants. At a sample size of 160, the study will have adequate power across a range of clinically meaningful effect sizes, operationalized as proportional reductions in D-dimer (relative to heparin) from 20% to 40% in increments of 5% (see below). This sample size was selected, based on a statistical simulation using Wilcoxon rank sum and assuming a 20% missing/dropout rate, to ensure inferences for the primary endpoint analysis will be robust, given certain potential confounding factors such as missing data (random or non-random), heterogeneous application of heparin (low molecular weight and unfractionated; prophylactic and therapeutic), effects of subject-level covariates (e.g., comorbidities), and effects of site-level covariates (e.g., country).

Power, Primary Endpoint							
	Effect Size (Proportional Reduction)						
	Enrolled Subjects	Evaluable Subjects	20%	25%	30%	35%	40%
Sample Size	80	64	55.8%	67.4%	75.6%	81.0%	84.5%
	100	80	60.5%	72.7%	80.1%	84.9%	87.8%
	110	88	63.6%	76.2%	80.7%	86.6%	89.2%
	120	96	65.2%	78.0%	82.8%	86.9%	91.0%
	130	104	68.2%	79.3%	84.8%	88.7%	91.7%
	140	112	68.9%	80.7%	86.6%	89.3%	92.5%
	160	128	71.3%	83.1%	88.3%	91.3%	94.1%
	180	144	74.9%	84.5%	89.5%	92.5%	94.6%
	200	160	77.2%	86.5%	91.0%	93.8%	95.8%

*Significance via $\alpha = 0.05$
 †Simulated with 20% Missing Data
 ‡Percentages as Averages Across Other Simulation Conditions

2.3 Participant Selection, Randomization, and Blinding/Unblinding

Approximately 160 participants 18 to 90 years of age with COVID-19 documented by a validated test such as polymerase chain reaction (PCR) within 1 week of hospitalization or screening and D-dimer above the upper limit of normal will be eligible for the Phase 2b study.

Participants will be randomly assigned 1:1:2 to receive rNAPc2 at one of 2 dose regimens, or a heparin regimen per site SoC (prophylactic or therapeutic). The higher rNAPc2 dose regimen will include a 7.5 µg/kg subcutaneous (SC) loading dose on Day 1 followed by 5µg/kg SC on Days 3 and 5; the lower dose regimen will be administered as a 5 µg/kg SC loading dose on Day 1 followed by 3µg/kg SC on Days 3 and 5. Prophylactic or therapeutic doses of low molecular weight heparin (LMWH) or unfractionated heparin (UFH) will be prescribed in the control group as per local SoC. Participants will be stratified by local laboratory D-dimer level at screening (\leq or $> 2\times$ the assay’s upper limit of normal (ULN)).

The NAPc-201/301 study utilizes a modified Prospective Randomized Open-Label, Blinded Endpoint (PROBE) design. In a traditional PROBE design, the participant and investigator are aware of treatment assignment, but endpoints are classified by blinded adjudicators. In the ASPEN trial, the site investigator(s) and research coordinator(s), as well as the treating clinical team are aware of treatment

assignment, but the randomized participants will not be told their treatment assignment and all efforts will be made at the site to keep them blinded in order to minimize bias in safety and clinical endpoint reporting. In addition, adjudicators of clinical events will be blinded to treatment assignment as well as other information relevant to unblinding in order to minimize any potential bias in event categorization. To support the integrity of study results, blinding of study management personnel (Sponsor, Contract Research Organization/Academic Research Organization, Oversight Committees, etc.) will be managed at the study role level as described in the Blinding Plan. Additionally, neither the study site, Sponsor, CEC, nor study participants will have access to the central laboratory results during the conduct of the trial with the exception of clinical safety alerts. The investigator will not be provided with randomization codes. The study site will know the treatment assignment; however, participants should not be made aware of their treatment assignment.

2.4 Primary Endpoints

2.4.1 Efficacy

The primary efficacy endpoint is proportional change, represented as percent change, in D-dimer level from baseline to Day 8 or Day of Discharge if prior to Day 8.

Language pertaining to the primary efficacy endpoint in the ASPEN Protocol is operationalized as proportional change.

2.4.2 Safety

The primary safety endpoint is major or non-major clinically relevant bleeding within eight (8) days of randomization as compared to heparin.

2.5 Secondary Endpoints

2.5.1 Efficacy

Secondary efficacy endpoints are:

- Change in D-dimer level from baseline to 24 hrs post the institution of study medication following randomization (Study Day 2), and 48 hours after institution of study medication (Study Day 3)
- Probability of discharge as assessed by ACTT ≥ 6 by Day 8 and Day 30 post randomization
- Composite of death, thrombosis, organ support, or rehospitalization within 30 days adjudicated as to its relatedness to COVID-19
- Change in biomarkers associated with outcomes including those related to coagulation and inflammation from baseline through Day 8

2.5.2 Safety

Secondary safety endpoints are:

- Major or non-major clinically relevant bleeding with rNAPc2 vs. heparin
- Bleeding with higher vs. lower dose rNAPc2 through Day 30
- Other adverse events (AEs)

3 Data Set Specifications

3.1 Database Description

The following data sources will be used to create the final study tables, figures, and listings (TFLs).

- Protocol Deviation database which will store protocol deviations
- Clinical Endpoint Adjudication database which will store all adjudicated review fields and outcomes
- Central laboratory data from PPD
- Clinical database which will store all other data used for analysis

These databases are hosted by the following systems:

- Protocol Deviation database: DATATRAK UX CTMS
- Adjudication database: AG Mednet
- Central lab data from PPD transferred to CPC as SAS dataset
- Clinical database: DATATRAK UX EDC™

Separate data management and adjudication plans will describe the set-up and management of these databases including preparing and selecting data for study analysis. The adjudication, laboratory and clinical databases will be reconciled to ensure within- and cross-form consistency.

3.2 Creating Analysis Data Sets

To facilitate the analysis of study data, it will be necessary to extract and combine the relevant variables from the data sources described above. All analysis data sets will be generated using SAS software (SAS and all other SAS Institute Inc. products or service names are registered trademarks of SAS Institute Inc., Cary, NC, USA).

3.3 Generation and Validation of Data Analysis Programs and Output

Programming and output developed prior to the database lock will be produced and displayed using dummy treatment codes to protect the integrity of the study and minimize any unintended bias in accordance with the Study Blinding Plan.

3.4 Archiving Data and SAS Files

Following final database lock, the SAS® programs used to analyze data for the final Clinical Study Report (CSR) will be executed and archived.

4 Considerations and Methodology

The analysis of data for the study will be based on the objectives and endpoints outlined in the protocol. Final analysis will be produced on locked clinical study data using SAS version 9.4 or higher.

Minor edits and additions which do not affect the content or meaning of either the text or mock shells (e.g., typos, spacing, etc.) will not constitute the need for an amendment to this plan. Major changes to this reporting plan will require an amendment and will require approval. All changes which are made to the reporting plan from the initial approval will be tracked on a Programming Changes Log.

4.1 Reporting Timeframes

This reporting plan describes the required output for final reporting for the Phase 2b study and will occur when all participants have completed the Phase 2b study and those data have been cleaned and locked according to the Data Management Plan (DMP).

Interim reporting of efficacy and safety data to a DSMC, including planned interim analyses, will be described in the DSMC charter and a separate reporting plan.

4.2 Analysis Display Conventions

General conventions for statistical analyses are pre-specified. Departures from these general conventions may be given in the specific detailed sections of this SAP. When this occurs, the rules set forth in the specific section take precedence over the general convention.

- All tables will have the population sample size for each dosing group in the column heading.
- Continuous variables will be summarized using the standard display of n, mean, standard deviation (SD) medians, minimum, and maximum, first and third quartiles for participants with non-missing data.
- Ordinal or categorical variables will be summarized using the number and percentage of observed response in each category.
- Summary statistics for discrete variables will consist of the number and percent of responses in each category. The count and percentage of responses will be presented in the form of XX (XX.X%), where the percentage is in parentheses. If the count is “0” then the percentage may not be presented. If the percentage is “100”, the decimal place may be dropped. In addition, the decimal place may also be dropped due to space constraints within a table where there is no impact on interpretation. Denominator for percent will be footnoted if not the population size in the column heading.
- Leading zeros will be used for decimal values less than one. For example, use “0.05” rather than “.05.”
- *P* values will be presented as 4 decimals (e.g., “0.0054”) or replacing the leading 0 with “< .0001” and “> .9999” if applicable.
- A participant’s age will be calculated using birth date and informed consent date. Age will be reported in years and rounded to the lowest (floor) integer.
- Body Mass Index (BMI) calculation is based on the formula below:
$$\text{BMI (kg/m}^2\text{)} = \text{Weight (in kg)} / \text{Height}^2 \text{ (in meters)}$$
- All medical history and AEs will be coded using Medical Dictionary for Regulatory Activities (MedDRA) as described in the DMP.
- All medications will be coded using the World Health Organization Drug Dictionary [Enhanced] (WHO DDE) as described in the DMP.

4.3 Determination of Study Day

The day the participant is randomized will be considered study “Day 1.” The day prior to randomization will be considered study “Day -1.” There will be no Day 0. If the start day is missing the first day of the month will be used.

If the start year or stop year is missing it is assumed the medication was taken concomitantly with study drug.

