5.5 STRATEGIES FOR RECRUITMENT AND RETENTION

The target sample size for Phase 2b is approximately 160 participants, with an additional approximately 450 planned during Phase 3. Eligibility criteria are broad to facilitate enrollment, the primary requirement being elevated D-dimer. In published data, 68% of patients hospitalized with COVID-19 had D-dimer > 0.5 ng/mL.³²

Enrolled participants are anticipated to reflect the epidemiology of COVID-19. In May 2020, 46%, 30% and 24% of hospitalized patients with COVID-19 in the US were >65, 50-64 and <50 years of age, respectively. Race/ethnicity was reported as 37% Non-Hispanic White, 40% Non-Hispanic Black and 14% Hispanic. Concomitant medical conditions included hypertension 59%, CV disease 35%, metabolic disease 42%, obesity 50% and renal disease 16%.²⁹

We anticipate enrolling at approximately 20 sites in Phase 2b and 80 clinical sites in Phase 3, selected for experience providing high quality clinical trial data and for the prevalence and ability to recruit the target population. Sites will be selected in geographic areas with high rates of COVID-19 in the US and abroad. Because of the rapid timeline, regulatory approval and drug importation time will be considered during site selection.

Adherence is facilitated by planned administration of all study medication in-hospital. Retention should be facilitated due to the short duration of follow up and limited number of study-related activities. Follow up for clinical outcomes and AEs may be conducted remotely.

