5.3 Subgroups

For the primary efficacy endpoint, the treatment effects across the following subgroup factors will be examined:

- D-dimer randomization stratification factor ($>$ vs. $\leq 2x$ local laboratory ULN)
- Treatment with an agent with demonstrated efficacy in patients with COVID-19, as described in [Section 6.2.1](#) (yes, no)
- Background antiplatelet therapy at baseline, as described in [Section 6.2.1](#)
- rNAPc2 dose regimen
- Initial heparin dosing strategy (prophylactic vs. therapeutic; within regimen comparison only)
- Severity of disease (as defined in [Section 14.1](#))
- Source of Laboratory Values used for primary endpoint determination (central vs. local)

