8.2.3 Other Adverse Events

Safety assessments will also include monitoring of serious adverse event(s) (SAE) and non-serious adverse event(s) (AE). Efficacy and safety endpoints that are adjudicated positively as study outcomes, including all bleeding events, will not be considered as AEs or SAEs.

All AEs will be collected from the time of randomization until the participant completes Day 30 or final contact, whichever is longer. All SAEs will be collected from the time of consent until the participant completes Day 30 or final contact, whichever is longer.

All reported AEs will be coded using the Medical Dictionary for Regulatory Activities (MedDRA).

Participant counts will be summarized using frequencies and percentages. A participant will be counted only once per category of summarization (e.g., if a participant has multiple AEs, the participant will only be counted once in the overall 'Any AE' row and will be counted once in each row for the specific AE category reported). Where participants have more than one level of severity/relatedness recorded only the highest level of severity/relatedness will be summarized.

Participant counts will be summarized by system, organ class and preferred term (PTm) by treatment group for treatment-emergent AEs (TEAEs) and by seriousness, relatedness.

An AE identified by the investigator as 'Related' or 'Potentially Related' or where relationship is missing will be considered 'related to study treatment.'

All AEs will be listed. Listings of SAEs, Related AEs, fatal and AEs of special interest (e.g., Overdose, misuse, or accidental exposure to study drug; medical error involving study drug), will also be listed. Additional details of SAEs and Deaths will also be listed.

Treatment Emergent is defined as any SAE/AE that has a start date during or after administration of the investigational product (i.e., randomized rNAPc2 or heparin treatment), post-randomization up to Day 30 or final contact.

Data will be displayed as collected in the clinical database. Adverse Events with missing start dates will be considered as treatment emergent.

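### The SAP's first-of-month rule for a missing start day can date a post-randomization start before Day 1, which can falsely flag baseline antiplatelet therapy and leaves partial-date adverse events without a clear rule

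*SAP*

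**What the plan says.** SAP 4.3 makes the day of randomization Day 1, with no Day 0, and then states: "If the start day is missing the first day of the month will be used". No data type is named and there is no lower limit at randomization or first dose. The next sentence concerns drugs only: "If the start year or stop year is missing it is assumed the medication was taken concomitantly with study drug".

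For adverse events, SAP 8.2.3 gives a definition, "Treatment Emergent is defined as any SAE/AE that has a start date during or after administration of the investigational product", and its own default: "Adverse Events with missing start dates will be considered as treatment emergent". It does not mention a date with month and year known and only the day missing. Non-serious events are collected from randomization and serious events from consent. All adverse events are listed.

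For drugs, SAP 6.2.1 calls a medication prior only when start and end both precede Day 1. A start before Day 1 with a blank end is ongoing and concomitant. SAP 5.3 lists among the primary-endpoint subgroups "Background antiplatelet therapy at baseline, as described in" Section 6.2.1.

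**The concern.** A first-of-month rule is harmless when the month is clearly before or after randomization. It goes wrong in the randomization month itself, because the 1st precedes Day 1 for everyone not randomized on the 1st. Two things are at stake.

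- **Drugs.** An antiplatelet agent started after randomization can acquire a start before Day 1 and be read as background therapy. A baseline subgroup factor would then contain post-randomization information.
- **Adverse events.** If the rule is applied to them, an event in the randomization month with an unknown day fails the treatment-emergent definition, while an event with no date at all passes it. The better-documented event would be handled less conservatively.

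Partial dates are plausible after discharge, since Protocol 5.5 says "Follow up for clinical outcomes and AEs may be conducted remotely". That remote collection produces more of them is an inference; the documents give no rate.

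**Working it through.** The plan states no figure that depends on this rule, so there is none to reproduce. The check enumerates calendar dates.

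**Inputs.** From SAP 4.3: Day 1 is randomization, and a missing day becomes the 1st. From SAP 8.2.3: adverse events are collected to Day 30 or final contact. Assumptions: randomization is spread evenly over a 365-day year, onset is spread evenly over the stated days, and first dose is on the day of randomization.

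**Rule.** The imputed date falls before Day 1 exactly when onset is in the randomization month and randomization was not on the 1st.

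**Result, among starts with only the day missing**

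| True onset | Before Day 1 | On Day 1 | After Day 1 |
|---|---|---|---|
| Days 1-8 | 85.2% | 3.3% | 11.5% |
| Days 1-30 | 49.1% | 3.3% | 47.7% |

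**Cross-check.** The chance that an onset t days after randomization is in the same month is about 1 - t/30.4. The mean over t = 0 to 7 is 1 - 3.5/30.4 = 0.885. The mean over t = 0 to 29 is 1 - 14.5/30.4 = 0.523. Subtracting randomizations on the 1st, 12/365 = 0.033, gives 0.852 and 0.490, in agreement with the table.

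**Later onsets.** For Days 9-30 the share is (30 × 0.4907 - 8 × 0.8521)/22 = (14.72 - 6.82)/22 = 0.36.

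**Dependence on randomization date.** In a 31-day month, the number of the 30 onset days moved before Day 1 is 0 if randomized on the 1st, 30 on the 2nd, 17 on the 15th and 4 on the 28th.

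**Share of all records moved.** The proportion lacking only the day is not in the documents, so a range is assumed.

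| Only day missing (assumed) | 0.5% | 1% | 2% | 5% | 10% |
|---|---|---|---|---|---|
| Days 1-8 onsets moved | 0.4% | 0.9% | 1.7% | 4.3% | 8.5% |
| Days 1-30 onsets moved | 0.2% | 0.5% | 1.0% | 2.5% | 4.9% |

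For adverse events these are upper limits, because the text allows three readings:

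1. 8.2.3 covers partial dates. The event is treatment-emergent and nothing is lost.
2. 4.3 fills the day first. The date is then complete and can precede first dose, so the event leaves the treatment-emergent tables but stays in the listing.
3. 4.3 is for drugs only and 8.2.3 only for wholly missing dates. No rule then covers a partial adverse event date.

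**Drugs, under 6.2.1.** A moved drug with a blank end stays concomitant. One that ends on or after Day 1 does not meet the definition of prior. What remains is a false start before Day 1, which matters wherever baseline status is read from dates. Neither 5.3 nor 6.2.1 says how that status is derived.

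**After the fix.** With the Day 1 date imputed when month and year match, 0 of 10,950 enumerated onsets (365 × 30) fall before Day 1. The cost shows on the other side: 86.8% of true starts in the seven days before randomization lie in the randomization month and would move to Day 1 unless other information places them earlier.

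**The case against.** The strongest reply is that 4.3 was never meant for adverse events. It does not name them, its next sentence is about medication, and 8.2.3 has its own default. SAP 4.2 says of departures from general conventions: "When this occurs, the rules set forth in the specific section take precedence over the general convention". SAP 8.2.3 also says adverse event data are displayed as collected, which points away from imputing them. This stands in part. A reader might infer that 4.3 removes adverse events from the treatment-emergent tables; the documents do not support that as a settled effect. Precedence does not close the question, however, because it helps only if 8.2.3 covers partial dates, and 8.2.3 does not say so.

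A reader might also infer that the primary results are at risk. They are not. SAP 8.2.3 and Protocol 8.3 keep bleeding events out of the adverse event tables, so this route does not reach the primary safety endpoint. The primary D-dimer comparison does not use adverse event or drug start dates.

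Nor do drugs drop out of the concomitant summaries when the end date is blank, and not every drug subgroup is exposed. Only the antiplatelet factor is tied to baseline; the factor for agents with demonstrated efficacy in COVID-19 is not.

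Finally, the schedule of activities in Protocol 8.1.1 calls for at least daily assessment in hospital, so missing days should be fewest early on. The 85% figure therefore applies where partial dates are least likely; for Days 9-30 the share is about 36%. This limits the size of the problem but leaves the wrong date in place.

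**Conclusion.** The rule in 4.3 as written can put a post-randomization start before Day 1. Among day-missing starts this affects about 85% of Days 1-8 onsets and 49% of Days 1-30 onsets, assuming uniform randomization and onset dates. It affects none when randomization was on the 1st or onset was in a later month. The absolute number is unknown because the documents give no rate of partial dates, and it is probably small in hospital.

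For drugs, the consequence is a possible false baseline flag in one subgroup factor. For adverse events, it is a conflict or gap between 4.3 and 8.2.3 that the programmer would have to resolve without guidance; on one reading, events leave the treatment-emergent tables while remaining listed. This is a cheap correction worth making before database lock, and it does not threaten the primary analyses.

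**What to change.** - **SAP 4.3.** If only the day is missing and month and year match those of first dose, impute the first-dose date, or the stop date if that is earlier. Otherwise use the 1st of the month.
- **SAP 8.2.3.** State that an adverse event with a partial start date is treatment-emergent unless its known date parts or its stop date show onset before first dose.
- **SAP 5.3 and 6.2.1.** Take baseline therapy from the screening/baseline medication record, not from imputed dates. This also protects true pre-randomization drugs that the new 4.3 rule would otherwise move to Day 1.

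The cost is SAP wording and a few lines of date-imputation code. The downside is that a true pre-dose serious event (these are collected from consent) in the first-dose month, with only its day missing and no stop date showing earlier onset, would count as treatment-emergent. That error is in the conservative direction.
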